Patients with castrate-resistant, metastatic prostate cancer, with evidence of progressive disease by scans (but not by pain symptoms) or rising PSA, who may or may not have been previously treated with other therapies (including chemotherapy, abiraterone, or enzalutamide), will be invited to participate. Subjects will be randomly assigned to a treatment group for the first two study arms. Once at least 12 evaluable subjects have been accrued to Arms 1 and 2, and once Arm 3 is open to accrual, Arms 1 and 2 will be closed and all further accrual will be to Arm 3. Given the absence of significant adverse events observed in previous clinical trials with pTVG-HP, no adverse events > grade 2 are anticipated related to that agent. While not common, previous immune-associated toxicities have been observed with pembrolizumab, including immune-mediated pneumonitis, colitis, hepatitis, hypophysitis, nephritis, hyperthyroidism, and hypothyroidism. Hence these may

be anticipated events. In 89 patients treated with pembrolizumab at 2 mg/kg every 3 weeks in a study of patients with unresectable or metastatic melanoma, < 20% of patients experienced any adverse reaction > grade 2; the most common adverse reaction was fatigue (7% of patients). Three grade 4 laboratory abnormality events (hyperglycemia, increased ALT, and anemia) were reported. In a larger trial of 411 patients with advanced melanoma, 9% of patients discontinued treatment due to adverse reactions. However, patients in the approval trial received a median of 9 doses, more doses than will be used in the current trial. In the current trial patients will be evaluated for evidence of toxicity, and further accrual to a specific treatment arm will be discontinued if the toxicity rate is deemed to be excessive for that arm. Given the more limited exposure to this agent (4 doses total), a toxicity rate of 35% for Grade 3 events or 20% Grade 4 events given an attribution of at least possibly related to study treatment will be considered excessive. Grade 3 limited site reactions (lasting < 48 hours) and fevers/chills (lasting < 48 hours) will be excluded from this assessment, as expected possible adverse events of limited duration from vaccination.

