Evidence that the toxicity rate is excessive will be considered sufficient if, within any arm, the lower limits of the 90% one-sided confidence intervals for the estimates of the true toxicity rates exceed the toxicity limits defined above (i.e., 35% for Grade 3 events and 20% for Grade 4 events), after the first 5 patients have been accrued. Operationally, this will occur if any of the following events occurs within a study arm: Grade ≥ 3 events are present in at least 4 out of the first 5, 5 out of the first 7 (or less), 6 out of the first 10 (or less), or 7 out of the first 12 (or less) or 8 out of the first 14 (or less) or 9 out of the first 16 (or less) of the subjects accrued (within a study arm). Furthermore, accrual will be temporarily suspended if any of the following events occur: Grade 4 events are present in at least 3 out of the first 5, 4 out of 9 (or less), 5 out of the first 13 (or less) or 6 out of 16 (or less) of the subjects accrued (within a study arm).

If one of these thresholds is reached, accrual will be temporarily suspended and the study will be reviewed for safety, dose modification and safety modification, and the study will be reviewed for safety by the UW DSMC (data and safety monitoring committee) with respect to treatment arm. Once the study is suspended, it would only be reopened if modifications could be made, and approved by the DSMC and the UW-IRB, to assure that patient safety is reestablished. If not, the study would be closed.

B. Endpoints

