The expected 6-months progression-free survival rate in Arm 2 (pembrolizumab is administered sequentially after pTVG-HP) is 25%. It is hypothesized that the treatment of pTVG-HP, when administered concurrently with pembrolizumab (Arm 1), will result in a substantial increase in the 6-month progression-free survival rate. Specifically, it is anticipated that the 6-month progression-free survival rate in Arm 1 will be at least 65-75%. The following table shows the required sample sizes for detecting various differences in the 6-month progression-free survival rates between the two study arms, assuming 80% power and a one-sided 0.10 significance level. Since this is a pilot study, a less stringent significance level of 0.10 rather the traditional 0.05 level will be used for the primary efficacy evaluation.

	6-month progression free survival rate Arm 1			
6-month progression free survival rate Arm 2	0.65	0.70	0.75	0.80
0.20	15	11	10	9
0.25	17	15	11	10

A sample size of 15 patients per arm is proposed. This sample size will provide 80% power to detect an anticipated absolute difference of at least 45% (e.g., 25% vs. 70% or 20% vs. 65%) in the 6-months progression free survival rates between the two arms. These calculations are based on Fisher’s exact test. Furthermore, the proposed sample size of 15 patients per arm is also sufficient to provide accuracy in estimating toxicity rates. Specifically, the toxicity rates (i.e., of grade ≥ 2, grade ≥ 3, grade 4 toxicities) for each arm will be estimated with a standard error of less than 15% and the 95% confidence interval of the toxicity rates will be no wider than 45%. The probability of observing at least one event of a serious adverse event within a study arm is >95% if the adverse event rate is 20%. Analogously, the probability of observing at least one event of serious adverse event is at least 79% if the adverse event rate is only 10%.

In order to account for unevaluable (for efficacy evaluation) patients, 32 eligible patients (16 per arm) will be accrued and randomized. Based on past experience with this patient population treated at our institution, we anticipate that the proposed total number of 32 patients will be accrued within 18 months.

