A total sample size of 20 evaluable patients is proposed for the extended treatment Arm 3 to evaluate the median time to radiographic progression. The proposed concurrent administration schedule will be considered as ineffective if it results in a median time to radiographic progression of 3 months or less. Hence, the null hypothesis that the median time to radiographic progression is at most 3 months will be tested against the alternative hypothesis that the median is greater than 3 months. A median time to radiographic progression of 6 months or more, on the other hand, will be considered as promising to warrant further clinical evaluation of the proposed concurrent administration schedule. With the proposed sample size of 20 evaluable patients for the extended treatment Arm 3, a median time to radiographic progression of 6 months will be detected with 90% power at the one-sided 0.05 significance level, assuming an accrual period of 12 months with a uniform accrual pattern and a minimum follow-up period of 12 months. Furthermore, a total sample size of 20 evaluable patients is also proposed for the extended treatment Arm 4, to evaluate the median time to radiographic progression for this study arm. The null hypothesis that the median time to radiographic progression is at most 3 months will be tested against the alternative hypothesis that the median is greater than 3 months. With the proposed sample size of 20 evaluable patients for the extended treatment Arm 4, a median time to radiographic progression of 6 months will be detected with 90% power at the one-sided 0.05 significance level, assuming an accrual period of 12 months with a uniform accrual pattern and a minimum follow-up period of 12 months. Furthermore, the proposed sample size of 20 patients for both Arm 3 and Arm 4 is adequate to estimate toxicity rates within each arm with sufficient accuracy. Specifically, toxicity rates will be estimated with a standard error of less than 12% and the corresponding two-sided 95% confidence intervals will be no wider than 40%.

NaF PET/CT will be obtained in 6 - 10 patients with known osteoblastic metastases at baseline, week 6 and week 12. This sample size will provide at least 80% power to detect moderate to large effect sizes ranging from 1.0-2.0 for the differences in SUV metrics between time points at the two-sided 0.05 significance level.

F. Analysis

F.1. General

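### The toxicity suspension counts in Section 6.A stop at patient 16, although Arms 3 and 4 plan 20 evaluable patients each, and the Grade 4 count at patient 6 is one event higher than the plan's own rule gives.

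*Combined protocol and SAP*

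**What the plan says.** Section 6.A (Study Arm Assignment and Toxicity Assessment) treats toxicity as excessive in any arm if, once 5 patients have been accrued, "the lower limits of the 90% one-sided confidence intervals for the estimates of the true toxicity rates exceed the toxicity limits defined above". The limits are 35% for Grade 3 and 20% for Grade 4. No interval method is named.

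The section then gives the counts that put this rule into operation.

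- Grade 3 or higher: 4/5, 5/7, 6/10, 7/12, 8/14, and finally "9 out of the first 16 (or less) of the subjects accrued (within a study arm").
- Grade 4: "Grade 4 events are present in at least 3 out of the first 5, 4 out of 9 (or less"), then 5/13 and 6/16.

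The action follows from the counts: "If one of these thresholds is reached, accrual will be temporarily suspended and the study will be reviewed for safety".

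Section 11.E gives the arm sizes. For Arms 1 and 2, "32 eligible patients (16 per arm) will be accrued and randomized". For the later arms, "A total sample size of 20 evaluable patients is proposed for the extended treatment Arm 3", and "a total sample size of 20 evaluable patients is also proposed for the extended treatment Arm 4".

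The rationale for the limits in 6.A reads "Given the more limited exposure to this agent (4 doses total), a toxicity rate of 35% for Grade 3 events". The same paragraph says the approval trial's median of 9 doses exceeds what this trial will use. Section 6 allows up to 16 pembrolizumab doses in Arm 3 and 12 in Arm 4.

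**The concern.** The list ends where Arms 1 and 2 end, which suggests it was not revisited when Arms 3 and 4 were added. The rule in words has no upper patient number, but the suspension sentence refers to the listed thresholds, and none exists for patients 17 to 20. Study staff and the DSMC would have to derive those counts themselves, from an interval method the section does not name.

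Separately, the wording for 4 events in 9 or fewer patients sets the Grade 4 threshold at 4 for patient 6, where the stated rule gives 3.

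At stake is whether a safety trigger that the plan has already accepted is acted on in the two arms with the longest planned treatment. Safety is a primary objective.

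**Working it through.** **Inputs.** Limits of 35% and 20%, a one-sided 90% lower limit, and monitoring from patient 5 (Section 6.A). Arm sizes of 16 and 20 (Section 11.E).

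**Formula.** For x events in n patients, the exact lower limit is the 0.10 quantile of a Beta(x, n − x + 1) distribution. It exceeds the toxicity limit p₀ exactly when P(X ≥ x | n, p₀) < 0.10. The threshold at n is the smallest such x.

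**Step 1: reproduce the list, n = 5 to 16.** All 12 Grade 3-or-higher thresholds match, and 11 of the 12 Grade 4 thresholds match. Lower limits at the listed counts:

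| Grade ≥3 | Limit | Grade 4 | Limit |
|---|---|---|---|
| 4/5 | 41.6% | 3/5 | 24.7% |
| 5/7 | 40.4% | 4/9 | 21.0% |
| 6/10 | 35.4% | 5/13 | 20.05% |
| 7/12 | 36.2% | 6/16 | 21.0% |
| 8/14 | 36.9% | | |
| 9/16 | 37.5% | | |

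**Step 2: the mismatch, Grade 4 at n = 6.** P(X ≥ 3 | 6, 0.20) = 0.0989, below 0.10, and the lower limit for 3/6 is 20.09%, above 20%. So 3 events meet the rule and the list asks for 4.

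- Rounding does not explain it: 5/13 is even closer to the limit (20.05%) and is listed.
- The choice of interval does not explain it either. For 3/6 the one-sided 90% limit is 26.8% by Wilson, 20.5% by Wilson with continuity correction, 23.8% by Wald, 24.7% by mid-P and 26.4% by Jeffreys.
- Reading the rule as a two-sided 90% interval fails, because its exact form would need 4/5 for Grade 4 and 5/5 for Grade 3 or higher, against the listed 3/5 and 4/5.

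**Step 3: continue the rule to n = 20.**

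- Grade 3 or higher: 9 at n = 17 (35.04%), 10 at n = 18 and 19 (38.0%, 35.8%), 11 at n = 20 (38.5%).
- Grade 4: 7 at n = 17 to 20 (24.6%, 23.1%, 21.8%, 20.7%). 6/17 gives 19.7% and does not trigger.

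**Step 4: chance of a trigger in a 20-patient arm.** This is an exact recursion over patients, checking after each one from n = 5.

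| True rate | List as written | With 3/6 added | Full rule to n = 20 |
|---|---|---|---|
| Grade 4, 20% | 0.1575 | 0.1737 | 0.1907 |
| Grade 4, 35% | 0.6118 | 0.6262 | 0.6926 |
| Grade 4, 40% | 0.7503 | 0.7607 | 0.8242 |
| Grade ≥3, 35% | 0.1573 | n/a | 0.1831 |
| Grade ≥3, 50% | 0.5394 | n/a | 0.6205 |
| Grade ≥3, 60% | 0.8035 | n/a | 0.8726 |

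**Step 5: where the late gain arises.**

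- Grade 4 at 40%: first crossings at n = 18, 19 and 20 have probability 0.0143, 0.0227 and 0.0266. At 35% they are 0.0135, 0.0233 and 0.0295. There are none at n = 17.
- Grade 3 or higher at 50%: 0.0508 at n = 17 and 0.0303 at n = 19. At 60%: 0.0440 and 0.0251. There are none at n = 18 or 20.

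If exactly 20 patients are accrued, 3 remain to enrol after n = 17, 2 after n = 18, 1 after n = 19 and none after n = 20.

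**The case against.** The strongest reply is that no rule is missing, only a worked table. Section 6.A says accrual to an arm will stop if its toxicity is judged excessive, and defines excessive by the lower limit in any arm with no upper patient number. That covers patients 17 to 20 in principle, and this stands. It does not settle the matter, because suspension is tied to the listed thresholds. The only interval method the plan names for toxicity is Wilson, in 11.F.4.1 for the final 95% intervals, and Wilson gives a different Grade 4 count at n = 17 (6 rather than 7).

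The second reply is that the effect is small. This stands in part.

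- Adding 3/6 gains only 1.0 to 1.4 points at true rates of 40% and 35%. It matters only when exactly 2 of the first 5 patients have events and the sixth is the third.
- By January 2018 Arm 3 already had 11 patients and Arms 1 and 2 were to close before it (Section 2.F), so for future patients this correction can act only in Arm 4.
- Section 6.A cites three Grade 4 laboratory events in 89 melanoma patients. At a true Grade 4 rate of 10%, the trigger chance is 1.7% by the list and 2.3% by the full rule.

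The third reply is that Section 13 already describes weekly toxicity review and quarterly DSMC reports for gene-transfer trials, and the DSMC can suspend the study. That lessens the harm from a missed trigger but does not replace a pre-specified one. Treatment in Arms 3 and 4 runs to weeks 45 and 46, so a late trigger can still prompt a review that matters to patients on treatment.

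Finally, the 4-dose rationale changes no boundary. Nor is a median of 9 doses received directly comparable with maxima of 16 and 12. The statement of 4 doses in total still conflicts with Section 6.

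**Conclusion.** The concern holds. The operational counts do not implement the plan's own criterion in two places: they are absent for patients 17 to 20 in Arms 3 and 4, and they are one event too high for Grade 4 at patient 6. The first matters more. Of the 7.4-point shortfall for Grade 4 at a true rate of 40%, 1.0 point comes from patient 6 and the rest from the missing late entries. For Grade 3 or higher, the whole shortfall (8.1 points at 50%, 6.9 at 60%) comes from the missing entries.

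The practical effect is moderate. Much of the late gain arises with one or no patients left to enrol, where its value is chiefly DSMC review. The most useful missing entry is Grade 3 or higher at patient 17.

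The conclusion assumes exact binomial limits, inferred from their fit to the other 23 boundaries, a check after every patient, and accrual of exactly 20 per arm. The plan gives 20 evaluable patients, not the number accrued. The patient-6 finding does not depend on the interval method. The toxicity limits themselves are not in question.

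**What to change.** Replace the list in Section 6.A with counts computed from the existing criterion, and state that the limits are exact binomial:

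- **Grade 4:** 3 of the first 6 or fewer, 4 of 9, 5 of 13, 6 of 16, 7 of 20.
- **Grade 3 or higher:** 4 of the first 5, 5 of 7, 6 of 10, 7 of 12, 8 of 14, 9 of 17, 10 of 19. No entry is needed at 20, because 11 of 20 implies at least 10 of 19.

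If more than 20 patients may be accrued to obtain 20 evaluable, add 8 of 24 for Grade 4, and 11 of 21 and 12 of 24 for Grade 3 or higher. Their lower limits are 20.5%, 36.4% and 35.3%.

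The sponsor should also reconcile the 4-dose rationale in Section 6.A with the Arm 3 and Arm 4 maxima in Section 6.

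The cost is a short edit and slightly more temporary suspensions when the true rate sits at the acceptable limit: from 15.8% to 19.1% for Grade 4 at 20% (3.3 points, of which 1.6 come from 3/6), and from 15.7% to 18.3% for Grade 3 or higher at 35% (2.6 points).

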^e Tetanus immunization to take place any time after leukapheresis and prior to day 1

^f Where chemistry labs indicated, the following serum tests are to be performed: Chem 7 (sodium, potassium, bicarbonate, BUN, creatinine, glucose), ALT, AST, bilirubin, alkaline phosphatase, amylase, TSH (thyroid stimulating hormone), and LDH

^g Procedures can be +/- 7 days of this visit; scans to be done prior to biopsy (and study treatment for Arm 2)

^h Can be +/- 7 days of this visit

ⁱ Can be +/- 7 days of this visit, and not required if this is off-study visit and previous scans already confirmed disease progression

^j CT of chest at this time point only as clinically indicated

^k PT/INR only required for those subjects who will be undergoing a biopsy. May be performed up to 30 days prior to biopsy, required same day if subject is on coumadin^l If NaF PET/CT is available as standard of care procedure, this may be substituted for bone scan (bone scintigraphy), however all pre-treatment and post-treatment tests must use the same modality (NaF PET/CT or bone scintigraphy)

^m See section 9 for whether or not biopsy and FLT PET is required.

Plan of Treatment: ARM 3 – EXTENDED TREATMENT COHORT

Vaccine / Treatment Visit:	SCREENING		Day 1	Week 3 (21 +/- 3 days from Day 1)	Week 6 (21 +/- 3 days from week 3)	Week 9 (21 +/- 3 days from week 6)	Week 12 (21 +/- 3 days from week 9)	Week 15 (21 +/- 3 days from week 12)	Week 18 (21 +/- 3 days from week 15)	Week 21 (21 +/- 3 days from week 18)	Week 24 (21 +/- 3 days from week 21)	Week 27 (21 +/- 3 days from week 24)	Week 30 (21 +/- 3 days from week 27)	Week 33 (21 +/- 3 days from week 30)	Week 36 (21 +/- 3 days from week 33)	Week 39 (21 +/- 3 days from week 36)	Week 42 (21 +/- 3 days from week 39)	Week 45 (21 +/- 3 days from week 42)	END OF STUDY Week 48 (21 +/- 3 days after week 45)	28-Day Follow Up (28 +/- 7 days after off-treatment visit)
	Within 6 wks of day 1	Within 4 wks of day 1																		
History and Physical Exam																				
History	X																			
Consent	X																			
Physical Exam, ECOG PS		X	X		X		X		X		X		X		X		X		X	X
Tox assessment ^a		X	X	X	X	X	X	X	X	X	X	X	X	X	X	X	X	X	X	X
Lab Tests																				
CBC	X		X	X ⁱ	X ⁱ	X ⁱ	X ⁱ	X ⁱ	X ⁱ	X ⁱ	X ⁱ	X ⁱ	X ⁱ	X ⁱ	X ⁱ	X ⁱ	X ⁱ	X ⁱ	X ⁱ	X
Chemistry panel ^f	X		X	X ⁱ	X ⁱ	X ⁱ	X ⁱ	X ⁱ	X ⁱ	X ⁱ	X ⁱ	X ⁱ	X ⁱ	X ⁱ	X ⁱ	X ⁱ	X ⁱ	X ⁱ	X ⁱ	X
PT/INR		X ^k					X ^k													
Serum testosterone	X																			

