Patients will come off study at the time of radiographic (CT and/or bone scintigraphy) disease progression, with progression being defined only AFTER the first 3-month staging evaluation, at the time of undue toxicity (as defined below), or at the discretion of the patient and treating physician that continuing treatment is not in the best interest of the patient and/or that other standard therapies for prostate cancer are warranted due to symptomatic progression. Patients should be discouraged from discontinuing protocol treatment for PSA rise only. NaF and FLT PET/CT scans will be investigational and will not be used for making individual subject treatment decisions with respect to progression necessitating continuing or discontinuing protocol treatment. However, findings on NaF or FLT PET/CT that might pose medical risk to individual subjects will be communicated to the treating physician such that dedicated clinical imaging/intervention could be pursued, if necessary. Such findings on NaF or FLT PET/CT, by themselves, will not be used to define disease progression necessarily requiring patients to come off trial. Patients who, in the discretion of the treating physician, appear to be benefiting (e.g. declining serum PSA and/or

improvement in symptoms despite new radiographic lesions), may continue in protocol treatment/observation after discussion with the PI and study sponsor. Patients will continue to have blood drawn for immune studies, as per study calendar, up to one year after screening, even if off study prior to that time. Patients who undergo an initial research biopsy and/or NaF/FLT PET scan should also undergo the subsequent scans, as long as they are willing, even if they are off study prior to Month 3. In particular, evaluations performed at 6-month time point should be performed even if off-study prior to that time, if feasible. All subjects who have not come off study earlier for these reasons will come off study at the end of one year.

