A treatment-limiting toxicity will be defined as any Grade 3 or greater toxicity (using the NCI Common Terminology Criteria version 4, Appendix C), or a specific Grade 2 event as described below that affects agent dosing, with an attribution of at least possibly related to the study or treatment procedures, and occurring between the pre-study visit and within one month of the final study vaccine treatment or within 90 days of the last treatment with pembrolizumab (whichever is later). In general, if a patient develops Grade 3 toxicity with an attribution of at least possibly related to treatment (vaccine and/or pembrolizumab), the treatment schedule will be held until the toxicity resolves to Grade 1 or less. There will be no dose reductions due to adverse events. If a patient develops a second Grade 3 event both believed at least possibly due to treatment, or any Grade 4 event, no further treatments will be given. The patient will remain on study, however, with collection of radiographic and laboratory data as per protocol. The rationale for this is that patients could continue to benefit in terms of anti-tumor response and this could in fact be related to the development of other autoimmune toxicities. If the adverse event occurs during the initial 12 weeks (Arm 1) or 24 weeks (Arm 2) of treatment, a treatment delay of up to one week will be permitted, with the expectation that the event resolve to < grade 2 for retreatment, and that subsequent treatment will resume at the original study intervals. A delay > 1 week will result in a skipped dose/treatment. While rare overall, autoimmune events observed following pembrolizumab treatment of patients with melanoma typically resolved and did not necessarily lead to discontinuation of treatment.

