For patients specifically treated in Arms 3 or 4, the following management rules will apply: If a patient develops Grade 3 toxicity with an attribution of at least possibly related to pembrolizumab and unlikely related (or unrelated) to pTVG-HP vaccine, the pembrolizumab treatment will be held until the toxicity resolves to Grade 1 or less, with the vaccine schedule continuing as per protocol. If a patient develops a second Grade 3 event (or any Grade 4 event) believed to be at least possibly due to pembrolizumab, but unlikely related (or unrelated) to pTVG-HP vaccine, no further pembrolizumab treatments will be given. The patient will continue with pTVG-HP administration only as per protocol. However, if a patient develops a Grade 3 toxicity with an attribution of at least possibly related to pTVG-HP vaccine, both pTVG-HP and pembrolizumab treatment will be

held until the toxicity resolves to Grade 1 or less. If a patient develops a second Grade 3 event (or any Grade 4 event) believed at least possibly related to pTVG-HP vaccine, no further treatments will be given. The patient will remain on study, however, with collection of radiographic and laboratory data as per protocol. The rationale for these modifications is that patients could continue to benefit in terms of anti-tumor response and this could in fact be related to the development of other autoimmune toxicities, and patients who have toxicity from pembrolizumab could still potentially benefit from continued pTVG-HP vaccination.

Specific symptoms and potential adverse events that have been identified in previous trials with pembrolizumab are described below. Management for these specific conditions will be conducted as described, consistent with what has been previously recommended in the FDA prescribing information “package insert”:

Infusion-related reactions:

Treatment with pembrolizumab will be permanently discontinued for grade 3 or 4 infusion-related reaction.

Constitutional symptoms:

Mild, low-grade fevers and chills, and local skin site reactions, are expected events following immunization and/or treatment with GM-CSF. Grade 1 events will not be treated with anti-inflammatory agents unless they persist 48 hours after an immunization. Constitutional inflammatory events > grade 1, or persisting beyond 48 hours after immunization, will be managed with ibuprofen, if needed, up to 600 mg three times daily.

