6. Subjects will be observed for additional 30 minutes for unanticipated adverse events.
7. CT scan of abdomen and pelvis (CT of chest as clinically indicated), bone scintigraphy (can be performed +/- 7 days of this visit)

DD. Week 48 Visit (End of Study) (21 +/- 3 days after Week 45 visit):

1. Physical examination, symptoms assessment, and ECOG performance score.
2. Blood draw for CBC, chemistry panel, serum PSA and PAP (can be performed up to 3 days prior to this visit)
3. 10 ml peripheral blood (red-top tubes) for sera to evaluate antibody responses, and 100 ml peripheral blood (green-top heparinized tubes) for T-cell response evaluation and CTC analysis (can be performed +/- 7 days of this visit)
4. CT scan of abdomen and pelvis (CT of chest as clinically indicated), bone scintigraphy (can be performed +/- 7 days of this visit)

EE. 28-Day Follow Up Visit (28 +/- 7 days after Off-study date, if prior to week 48)

Patients will come off study at the time of disease progression, undue toxicity, or at the discretion of the patient and/or treating physician that it is not in the interest of the patient to continue treatment. A separate follow-up visit is not required for patients completing the week 48 evaluation, however for patients coming off study prior to week 48, 28-day follow up visit will include the following:

1. Physical examination, symptoms assessment, and ECOG performance score.
2. Blood draw for CBC, chemistry panel, serum PSA and PAP
3. IF NOT ALREADY COLLECTED WITHIN PREVIOUS 60 DAYS: 10 ml peripheral blood (red-top tubes) for sera to evaluate antibody responses, and 100 ml peripheral blood (green-top heparinized tubes) for T-cell response evaluation and CTC analysis

FF. Long-term Follow-Up

1. Subjects will be contacted by telephone (if not already being seen in clinic) annually for 2 years following the last DNA vaccination to collect clinical information to identify any potential long-term risks. This information has been requested by FDA for all gene delivery trials to assess potential long-term risks. The specific information to be collected annually will include:
 - Date of contact
 - Current medications
 - Hospitalizations (dates and reasons for hospital admission)
 - Stage of prostate cancer, treatments for prostate cancer, and recent serum PSA level
 - New cancer diagnoses
 - New autoimmune disorders
 - New hematologic or neurologic disorders
 - Other new medical diagnoses
 - Date of death if patient deceased

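### Sections 6.B, 9.EE and 9.PP take patients off study for undue toxicity, while section 8 keeps them on study with scans

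*Combined protocol and SAP*

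**What the plan says.** Three places make toxicity a reason to leave the study. Section 6.B, which covers all arms, takes patients off study "at the time of undue toxicity (as defined below"). Section 9.EE (Arm 3) and section 9.PP (Arm 4) both state: "Patients will come off study at the time of disease progression, undue toxicity, or at the discretion of the patient and/or treating physician".

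Section 8 states the reverse. For patients in general, after a second related Grade 3 event "or any Grade 4 event, no further treatments will be given", and then: "The patient will remain on study, however, with collection of radiographic and laboratory data as per protocol". The Arm 3 and 4 rules in section 8 repeat that sentence for vaccine-related stops. For toxicity attributed to pembrolizumab and not to the vaccine, they say: "The patient will continue with pTVG-HP administration only as per protocol".

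Section 6.B makes some provision for patients already off study. Immune blood draws go on for up to a year, patients who had a baseline research biopsy or PET are asked to have the follow-up one, and "evaluations performed at 6-month time point should be performed even if off-study prior to that time, if feasible".

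The 28-day visit has two anchors. The Arm 3 and Arm 4 calendars give "28-Day Follow Up (28 +/- 7 days after off-treatment visit"); section 9 gives "28-Day Follow Up Visit (28 +/- 7 days after Off-study date, if prior to week 48").

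**The concern.** A patient whose treatment is stopped for toxicity has a different follow-up schedule depending on which section the team reads. Under section 8 the scheduled scans continue. Under 6.B, 9.EE or 9.PP the patient is off study, and most of the scans are no longer named.

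Section 6.B makes time to radiographic progression the primary endpoint for Arms 3 and 4, and section 3.A includes it in a primary objective for all arms. Section 7.C.5 censors a patient without progression or death at the end of follow-up, so leaving the study for toxicity could set the censoring time. Section 8 justifies continued follow-up by suggesting that benefit may be linked to autoimmune toxicity. If so, censoring at toxicity is not independent of the endpoint.

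The scan at risk also differs between the randomized arms. By the calendars, Arm 1 receives pembrolizumab on days 1 to 64, so a stop can precede the month-3 scan that section 7.A makes the baseline for progression. Arm 2 receives it on days 85 to 148, with the month-3 scan done before the first infusion. A pembrolizumab-related stop there falls after the baseline and may cost the month-6 scan or later ones.

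**Working it through.** **1. Do the texts conflict?** Section 6.B points to a definition below it. The only matching text found is section 8, which defines treatment-limiting toxicity and gives the stopping rules. With that target, the same patient is off study under 6.B and on study under 8.

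**2. Does off study mean only off treatment?** Section 6.B writes separate exceptions for off-study patients (immune bloods, biopsy or PET, 6-month evaluations). These would be unnecessary if such patients kept the whole schedule.

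**3. Which scans are exposed?** Section 9 schedules CT and bone scan in Arms 1 and 2 at months 3, 6, 9 and 12, which is 4 time points after the start of treatment. The off-study text in 6.B names evaluations at 1 of them, month 6, subject to feasibility. The 28-day visit text in 9.EE and 9.PP lists no CT or bone scan. I place no weight on the calendars here, because their columns cannot be read reliably in the available text.

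**4. How many patients in Arms 1 and 2?** The documents give no count. Section 6.A cites two pembrolizumab figures from melanoma, and section 11.E plans 16 patients per arm, 32 in all.

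- Low: 3 Grade 4 laboratory events in 89 patients, assumed to be 3 different patients. 3/89 = 3.37%; × 16 = 0.54; × 32 = 1.08.
- High: 9% of 411 discontinued for adverse reactions. 0.09 × 16 = 1.44; × 32 = 2.88.

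Neither figure is the section 8 stopping rule, so they show order of size only. The 9% is probably high: section 6.A gives a median of 9 doses in the approval trial, against 4 here.

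**5. Arms 3 and 4.** The number could be zero. Toxicity attributed only to pembrolizumab leaves the patient on vaccine, section 6.A anticipates no vaccine-related event above Grade 2, and section 2.F attributes all events above Grade 2 to date to pembrolizumab.

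**6. Power, for scale only.** Section 11.E states 90% power per arm: 20 patients, median 6 against 3 months, one-sided 0.05, 12 months' accrual and 12 months' minimum follow-up. With exponential times and L = ln 2/6 per month:

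- Expected events = 20 × [1 − (e^(−12L) − e^(−24L))/(12L)] = 20 × [1 − (0.25 − 0.0625)/1.386] = 17.3.
- Power = Φ(√17.3 × ln 2 − 1.645) = 89.2%, which reproduces the stated 90% to within a point.
- Suppose 2 of 20 are censored early (9% × 20 = 1.8). At month 3: 18 × 0.865 + 2 × 0.293 = 16.2 events, power 87.3%. At month 6: 18 × 0.865 + 2 × 0.5 = 16.6 events, power 88.0%.

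This treats the censoring as non-informative. By step 5, two full stops per arm is probably too many. The result shows only that lost information is not the main issue.

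**The case against.** The strongest reply is that section 8 is the specific, reasoned rule and already answers the question; on that view 6.B and section 9 contain loose wording and nothing more. The protocol does use the terms loosely: week 48 ends the study for Arm 3 and ends treatment for Arm 4, and the 28-day visit has both anchors. This is a single-institution trial with weekly review of adverse events and progression, so sites cannot diverge. Section 6.B says all subjects are imaged every 3 months, the primary population is ITT, no passage censors explicitly at toxicity, and deaths are collected for two years after the last vaccination. The available text also breaks off within section 15.E on withdrawal, so a definition of undue toxicity there cannot be excluded.

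Much of this stands as a limit on size. A single team that follows section 8 has no problem, and the 6-month comparison is partly protected. The conflict itself remains. The 3-monthly imaging statement does not say whether it applies off study, and ITT analysis cannot supply scans that were never taken. A definition in 15.E would still leave three passages sending patients off study for toxicity. The waiver of the off-study scan after confirmed progression may imply one exit scan, but not continued follow-up.

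**Conclusion.** The concern holds and is minor. The current text gives two incompatible rules for radiographic follow-up after a toxicity stop. Applied as written, the 6.B and section 9 rule would lose progression follow-up in a possibly informative way. The exposure is roughly 0.5 to 1.4 patients per randomized arm (1.1 to 2.9 of 32), on the assumption that the cited melanoma rates give the right order of size, and possibly nobody in Arms 3 and 4. The size of any bias is unknown, and no power loss is claimed. The conclusion rests on reading section 8 as the target of the 6.B cross-reference and on 6.B's own exceptions showing that leaving the study drops scheduled scans.

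**What to change.** In sections 6.B, 9.EE and 9.PP, make toxicity a reason to come off treatment and not off study, and replace the undefined term with a reference to the section 8 stopping rules. State that scheduled CT and bone scans (including month 3) and laboratory tests continue until progression, death, withdrawal of consent or the end of the year, and that progression after a toxicity stop counts as an event. Anchor the 28-day visit in section 9 to the off-treatment visit, as the Arm 3 and 4 calendars already do. Leave the rules on which toxicity stops which agent as they are.

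The cost is a wording amendment. Section 8 already intends this follow-up and the visits are in the calendars, so the only burden is that a few patients attend already scheduled visits after stopping treatment.
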